8.4.5. Pregnancy

If a pregnancy in a female participant is reported, the investigator should inform GSK within 24 hours of learning of the pregnancy and should follow the procedures outlined in Section 10.4 (Appendix 4).

A pregnancy is not considered to be an SAE, although abnormal pregnancy outcomes or complications (e.g., spontaneous abortion, foetal death, stillbirth, congenital anomalies, ectopic pregnancy) are considered to be SAEs.

There is no requirement to collect pregnancy information from female partners of male participants.

8.5. Treatment of Overdose

There is limited experience with overdosage of belimumab. Adverse reactions reported in association with cases of overdosage have been consistent with those expected for belimumab.

Two doses up to 20 mg/kg administered 21 days apart by IV infusion have been given to humans with no increase in incidence or severity of adverse reactions compared with doses of 1, 4 or 10 mg/kg.

GSK does not recommend specific treatment for an overdose of belimumab.

In the event of a belimumab overdose, the investigator should:

1. Contact the Medical Monitor immediately.
2. Closely monitor the participant for AEs/SAEs.
3. Document the quantity of the excess dose as well as the duration of the overdosing.

Decisions regarding dose interruptions or modifications will be made by the investigator in consultation with the Medical Monitor based on the clinical evaluation of the participant.

8.6. Pharmacokinetics

Blood samples will be collected for measurement of serum belimumab concentrations according to schedules that depend on the paediatric cohort.

Table 1 PK visit days and sample times study participants

[figure not shown]
Day (Week)	Time (Related to Dosing of Study agent)
0	0-4 hours after the end of infusion
7 (Week 1)	Day 7 \pm 1 day
14 (Week 2)	Day 14 \pm 3 days (Before the start of infusion)
84 (Week 12)	Day 84 \pm 7 days (Before the start of infusion and 0-4 hours after the end of infusion)

On days belimumab is administered and blood samples for pharmacokinetic analysis are obtained, participants may have an intravenous cannula inserted in the contralateral arm to the arm in which belimumab is administered for laboratory safety assessments and serial pharmacokinetic sampling. Blood samples for pharmacokinetic analysis should not be taken from the same arm as that used for the administration of belimumab. Samples may be obtained by venepuncture. The actual date and time (24-hour clock time) of each sample will be recorded.

If sampling for PK is missed, the impact will be minimized by attempting to reschedule the missing PK sampling to ensure sufficient precision of PK characterization in Chinese paediatric patients:

- For the scenario that patients will miss the sample collection on visit 3 (Day 7 \pm 1 day), the PK sampling should be rescheduled to any feasible visit at 7 days after dosing with \pm 3 days window.
- For the scenario that patients will miss the sample collection on visit 4 (Day 14 \pm 3 days), the PK sampling should be rescheduled to any feasible visit at 14 days after dosing with \pm 7 days window.
- For the scenario that patients will miss the sample collection on visit 7 (Day 84 \pm 7 days), the PK sampling should be rescheduled to when patients take the next dose.

Please refer to the Study Reference Manual for PK sample collection, processing and shipping instructions.

8.8. Genetics

Genetic analysis will not be evaluated in this study.

8.9. Immunogenicity Assessments

The presence of antibodies to belimumab will not be evaluated in this study.

8.10. Health Economics

Health Economics/Medical Resource Utilisation and Health Economics parameters are not evaluated in this study.

9. STATISTICAL CONSIDERATIONS

9.1. Statistical Hypotheses

This is an open-label study. A descriptive approach will be used, and no formal inference is planned in this study. For primary efficacy evaluation, using the percentage of participants with ≥ 4 -point reduction from baseline in SELENA SLEDAI at Week 52 in the placebo group in a Phase 2 paediatric study (Study BEL114055) as target value to guide the analysis planned for Chinese PAC study. The target can be described as the observed proportion of patients with clinical benefit $> 43.6\%$ (the mean placebo group response rate estimate in study BEL114055).

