1. PROTOCOL SUMMARY

1.1. Synopsis

Protocol Title: A Multi-Center, Open-Label Study to Evaluate Safety, Efficacy and Pharmacokinetics of Belimumab Plus Standard Therapy in Chinese Paediatric Patients with Active Systemic Lupus Erythematosus (SLE)

Short Title: Open label study of belimumab plus standard therapy in Chinese paediatric patients with active SLE

Rationale: The purpose of this study is to evaluate the safety, efficacy and pharmacokinetics of belimumab (10 mg/kg) intravenous (IV) with standard therapy in Chinese paediatric patients aged 5 to 17 years with active SLE. This study is conducted to support the registration of IV belimumab in treating paediatric SLE indication in China.

Objectives and Endpoints:

Objectives	Endpoints
Primary	Primary
➤ To evaluate the safety and efficacy of belimumab IV in Chinese paediatric patients with SLE.	
Safety
 
➤ Incidence of adverse events of special interest (AESIs) through 52 weeks:
 
 • All Infections of special interest, including serious infections of special interest and opportunistic infections • Infusion related systemic reactions and anaphylactic reactions • Depression, suicidality • Malignancies 
Efficacy
 
➤ Incidence of patients with ≥ 4 points reduction from Baseline to Week 52 in SELENA SLEDAI

Secondary	Secondary
➤ To evaluate safety and tolerability of belimumab IV in Chinese paediatric patients with SLE	
➤ Incidence of AEs through 52 Weeks
 
➤ Incidence of SAEs through 52 Weeks

➤ To evaluate the efficacy of belimumab IV in Chinese paediatric patients with SLE	
➤ Incidence of patients with ≥ 4 points reduction from Baseline in SELENA SLEDAI by visit
 
➤ Change from Baseline to Week 52 in Physician Global Assessment (PGA)

Objectives	Endpoints
	
 ➤ Change from Baseline to Week 52 in Parent Global Assessment (ParentGA) ➤ Change from Baseline in daily prednisone equivalent dose at Week 52 ➤ Time to first flare/ first severe flare over 52 weeks

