9.2. Sample Size Determination

Focusing on serious infections, the incidence rate of the serious AE “Infections and Infestations” (SOC) was 7.5% (4/53 participants) in the 10 mg/kg-IV group of the global paediatric study (Study BEL114055).

Under the assumption that the incidence rate of the serious infections is 7.5%, it is calculated that a study with 65 participants will have more than 99.0% probability to observe at least one serious infection. Under this sample size, for any other adverse events, there are more than 90% probability to observe at least one event once the incidence rate is larger than 4%. Additionally, using the Exact method in PASS 2019 for the confidence interval (CI) around a single proportion: a sample size of 65 would have produced a 95% CI of [2.4%, 16.8%] when the incidence rate of the serious infections is 7.5%.

For the efficacy purpose, as one of the key efficacy endpoints, the estimated percentage of participants with ≥ 4 -point reduction from Baseline in SELENA SLEDAI at Week 52 is 54.7% in BEL114055. Using the Exact method in PASS 2019 for the confidence interval (CI) around a single proportion: a sample size of 65 would produce a 95% CI of [41.9%, 67.1%] when the estimate is 54.7%. Under the assumption that the percentage of participants with ≥ 4 points reduction from baseline in SELENA SLEDAI at week 52 is 54.7%, it is calculated by simulation that a study with 65 participants will have more than 95.0% probability to observe a percentage larger than 43.6%.

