9.4.2. Primary Endpoint(s)

9.4.2.1. Efficacy Analysis

All efficacy analyses will be performed on the ITT Population.

Endpoint	Statistical Analysis Methods
Primary (Efficacy)	
Endpoint:
 
Incidence of participants with ≥ 4-point reduction from Baseline to Week 52 in SELENA SLEDAI

Endpoint	Statistical Analysis Methods
	
Analysis:
 
Descriptive statistics with frequency, percentage and 95% CI will be used to summarise incidence of participants with ≥ 4-point reduction from Baseline to Week 52 in SELENA SLEDAI. Further, the corresponding results of the previous study (BEL114055) will be used to guide the evaluation of consistency for this efficacy endpoint collected on Chinese subjects.

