8. Study Assessments and Procedures	Removal of the wording "Procedures conducted as part of the participant's routine clinical management (e.g., blood count) and obtained before signing of ICF may be utilised for screening or Baseline purposes provided the procedure met the protocol-specified criteria and was performed within the time frame defined in the SoA".	To ensure the screening tests are conducted in same central lab and to maintain the consistency.
8.1 Screening Assessments	Addition of "chest X-ray" and "QuantiFERON-TB Gold Plus test" in screening assessments.	To keep it consistent with the requirement in exclusion criterion #25 and items in the SoA.

Section # and Name	Description of Change	Brief Rationale
8.4.1 Time Period and Frequency for Collecting AE and SAE Information	Specifies non-serious related AEs should be reported using ADR CRF to the sponsor pharmacovigilance team ([contact]) via email within 5 calendar days.	Reporting form and email box has not been defined.
8.6 Pharmacokinetics	
Removal of “0.5 mL” for the volume of blood samples.
 
Addition of wording on recording the actual date and time (24-hour clock time) of each sample.
 
Removal of the maximum amount of blood drawn for PK during this study is approximately 5 mL for each participant.
 
Replacement of “Study Procedures Manual” with “Study Reference Manual”.
	
The volume of blood samples will be provided in Study Reference Manual.
 
The requirement on recording the time of PK blood sampling has not been defined.
 
The overall volume of blood samples will be provided in Study Reference Manual.
 
To keep consistent on the document name.

9.1 Statistical Hypotheses	Addition of the target value of the primary efficacy endpoint.	For compliance with authority's requirement.
9.2 Sample Size Determination	Addition of sample size consideration for the target value.	For compliance with authority's requirement.
10.2 Appendix 2: Clinical Laboratory Tests	Addition of “Creatine phosphokinase (CPK)” test in Clinical Chemistry of Table 3.	The CPK test required for patients with myositis has not been defined in the Appendix.
10.5 Appendix 5: Liver Safety: Required Actions and Follow-up Assessments	In Note #4, addition of quantitative Hepatitis B DNA test if positivity for HBsAg and/or HBcAb.	Quantitative Hepatitis B DNA test is required when evidences indicative of Hepatitis B infection exist.

Section # and Name	Description of Change	Brief Rationale

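### Should the protocol also state the chance of meeting the 43.6% efficacy target when the true response rate is only 43.6%?

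*Protocol*

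**What the plan says.** Section 9.1 states that the study is open-label and descriptive, with no formal inference. It then takes the placebo response in BEL114055 as a value to guide the analysis: "The target can be described as the observed proportion of patients with clinical benefit" exceeding 43.6%. Section 9.4.1 repeats that no hypothesis is tested.

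Section 9.2 gives two figures for this endpoint, one directly after the other. The first is precision: "a sample size of 65 would produce a 95% CI of [41.9%, 67.1%] when the estimate is 54.7" per cent. The second is the chance of passing the reference value. It opens with its condition, "Under the assumption that the percentage of participants with ≥ 4 points reduction from baseline in SELENA SLEDAI at week 52 is 54.7" per cent, and concludes that the study "will have more than 95.0% probability to observe a percentage larger than 43.6" per cent.

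Section 9.4.2.1 fixes the analysis: "Descriptive statistics with frequency, percentage and 95% CI will be used to summarise incidence of participants" meeting the endpoint. It adds that the BEL114055 results will guide an evaluation of consistency. The Synopsis gives the regulatory setting: "This study is conducted to support the registration of IV belimumab in treating paediatric SLE indication in China". Appendix 12 lists, under Amendment 01, "Addition of the target value of the primary efficacy endpoint", and gives an authority's requirement as the reason.

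**The concern.** A decision rule is normally described at two points: where the treatment works as hoped, and where it does no better than the comparator. Section 9.2 describes this rule only at the first. A reader who works out the second finds that a regimen responding at exactly the historical placebo rate would pass about half the time. Many passing results would also have a 95% CI that still contains 43.6%.

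The study is single-arm and supports a registration, so 43.6% is the only placebo reference for the primary efficacy endpoint. A report that the target was met, set beside a quoted probability above 95%, might be taken as evidence of benefit over placebo. If the protocol invited that reading, its main efficacy statement would rest on a rule that separates poorly near the placebo rate.

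**Working it through.** **Inputs.** n = 65 and the planning rate 54.7% come from Section 9.2. The reference value 43.6% comes from Section 9.1. No alpha is set anywhere.

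**The rule in counts.** 0.436 × 65 = 28.34. Since 28/65 = 43.1% and 29/65 = 44.6%, an observed proportion above 43.6% means X ≥ 29.

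**The protocol's own figures.**
- P(X ≥ 29) = Σ C(65, k) p^k (1 − p)^(65 − k), summed from k = 29 to 65. At p = 0.547 this is 0.9603, and a simulation with 1,000,000 draws gives 0.9604. The stated figure of more than 95.0% is correct.
- The exact (Clopper-Pearson) 95% limits are the 0.025 quantile of Beta(x, n − x + 1) and the 0.975 quantile of Beta(x + 1, n − x). At x = 0.547 × 65 = 35.555 they are 0.4186 and 0.6709. The stated [41.9%, 67.1%] is correct.

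**The same rule at other true rates.**

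| True rate | P(X ≥ 29) |
|---|---|
| 30% | 0.9% |
| 35% | 6.9% |
| 40% | 26.2% |
| 43.6% | 48.2% |
| 50% | 83.9% |
| 54.7% | 96.0% |

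**Where the 48% comes from.** At p = 0.436 the expected count is 28.34 and the standard deviation is √(65 × 0.436 × 0.564) = 4.00. With a continuity correction, z = (28.5 − 28.34)/4.00 = 0.04, so the upper tail is about 48.4%, close to the exact 48.2%. The cut-off sits on the mean, so the tail is about one half by construction. It hardly depends on sample size: the same rule gives 47.5% at n = 58, 46.3% at n = 60, 45.0% at n = 62 and 49.5% at n = 63. The figure restates that a point estimate is being compared with a threshold.

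**Target and interval together.**
- 29/65 (44.6%): exact 95% CI 32.3% to 57.5%.
- 36/65 (55.4%): 42.5% to 67.7%.
- 37/65 (56.9%): 44.0% to 69.2%, the first interval to exclude 43.6%.

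At a true rate of 54.7%, P(X ≥ 37) = 0.4085. The chance of passing with an interval that still contains 43.6% is therefore 0.9603 − 0.4085 = 0.5518, which is 0.5518/0.9603 = 57% of passing results. Section 9.2 already signals this: its planning interval at the hoped-for estimate starts at 41.9%, below 43.6%.

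**What the plan would report.** Take 32/65 as an example (32/65 = 49.2%, between the two cases above). Section 9.4.2.1 requires the count, the percentage and the 95% CI. The reader would see an observed proportion above 43.6% and an interval that contains it. Nothing in Sections 9.1, 9.2, 9.4.1 or 9.4.2.1 turns that into a claim of superiority.

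**The case for a change.** The strongest opposing case is this. The protocol chose to set a threshold and to quote a probability of passing it. Having shown the favourable side of the rule, it should show the other side in the same place. The study has no concurrent control and serves a registration, so a passing result may be over-read. Two or three sentences would prevent that, with no change to target, sample size or analysis.

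Part of this stands. The 48.2% is correct and is not in the protocol. No sentence says how to read an observed proportion above 43.6% whose interval contains 43.6%. Printing the figure would do no harm.

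It does not amount to a defect. The stated probability carries its condition in the same sentence, so nobody is told that passing is 95% likely whatever the truth. The interval printed just before it shows the limited precision. The feared over-reading belongs to a future report and is not in this text. The protocol's stated logic also differs: Sections 2.1 and 4.2 rest efficacy on extrapolation from existing data with a phase 3 trial waived, and Section 9.4.2.1 speaks of consistency with BEL114055. How a descriptive estimate is discussed against its interval is commonly left to the SAP, which is not at hand.

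Only one remedy would alter a conclusion: withholding any statement of benefit unless the interval excludes 43.6%. That amounts to a test. At 37 or more of 65 it has a 2.1% chance of success at a true rate of 43.6%, and only 40.8% at the planning rate. Placing it in a study that disclaims testing, against a target added to meet an authority's requirement, is a debatable design choice. It would not correct an error.

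**Conclusion.** The concern does not hold. Both figures that Section 9.2 gives for this endpoint reproduce (96.0% against a stated more than 95.0%; 41.9% to 67.1%). No error rate is declared, so none is breached. The unprinted 48.2% follows almost automatically from comparing an estimate with a threshold at which the truth is assumed to lie, and disclosing it would change no result.

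This rests on three things. The calculations take 65 independent participants, all in the denominator; the Synopsis says approximately 65, and small departures barely move the figures. They treat 43.6% as a fixed reference, as the protocol does, and ignore the sampling error of the placebo estimate. The conclusion also assumes that the results are reported as Sections 9.1 and 9.4.2.1 describe, as an observed proportion with its 95% CI. A report that presented passing 43.6% as proof of benefit over placebo would go beyond the plan, and the fault would lie with that report.

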2.1. Study Rationale

The treatment strategy and medications for SLE are similar between adults (including Chinese) and paediatric patients [Stichweh, 2004; Thakral, 2016]. The existing data of belimumab in Western children (age 5-17 years), adults from Western and northeast Asia allow extrapolation of efficacy to Chinese paediatric patients at the approved dose of 10 mg/kg IV, leading to waiver of phase 3 clinical trial in Chinese paediatric population.

However, there is an absence of information on the safety and efficacy profile of Belimumab in Chinese paediatric SLE patients. The differences between China and Western countries in population density, environment and endemic pathogens may influence the infection rate and safety profile of belimumab in Chinese paediatric population. In addition, the pharmacokinetic profile of belimumab should be further investigated to demonstrate if exposure in Chinese paediatric SLE patients is similar to SLE paediatric patients in Western countries.

Based on a requirement from China's Centre for Drug Evaluation (CDE), GlaxoSmithKline intends to conduct a post approval commitment (PAC) study in Chinese paediatric patients. The objective of this study is to evaluate safety and efficacy of belimumab IV plus background standard therapy in Chinese paediatric patients with active SLE aged 5 to 17 years, and to characterise the pharmacokinetic profile in a subset of the study population.

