4.2. Scientific Rationale for Study Design

Recent and past studies consistently show that adult and paediatric SLE patients have increased serum B-lymphocyte stimulator (BLyS) levels [Cheema, 2001; Hong, 2009; Petri, 2008; Wang, 2008]. In SLE, the elevation of BLyS may contribute to the persistence of B-cell subsets that produce pathogenic autoantibodies or promote inflammation that would otherwise be prone to down regulation. Thus, a therapeutic strategy that involves an antagonist to BLyS may have therapeutic benefit in SLE. In addition, this therapeutic strategy of utilising a BLyS specific inhibitor, belimumab, proved successful with the positive results from 4 pivotal adult lupus studies. In general, paediatric SLE patients have more severe disease and thus higher disease activity index on an average than adults. Adult SLE patients who presented with disease that is more active performed better with belimumab. Based on this information, it is hypothesised, that belimumab will have a beneficial effect in the paediatric SLE population.

Results of phase 2 study (BEL110455) of belimumab in 93 paediatric SLE patients demonstrated similar efficacy and safety profile in paediatric and adult Western population. Belimumab was granted approval in the United states (US)/Japan/European Union (EU) in 2019 to extend the indication to paediatric patients aged 5 to 17 years with active SLE despite standard therapy.

The existing data thus allow extrapolation from Western paediatrics to Chinese paediatric patients at the approved dose of 10 mg/kg IV and a waiver of phase 3 clinical trial in Chinese paediatric population. However, there is an absence of safety and efficacy profile in Chinese paediatric SLE patients. Overall consistent steady-state average concentrations (Cavg_ss) were predicted in Chinese paediatric patients and Western/Chinese adults

based on a population PK analysis (GSK document number [2020N427517_00](#)).

However, the PK exposure of belimumab is to be further confirmed in Chinese paediatric SLE patients. To support the registration of paediatric SLE indication in China, PAC will be conducted to demonstrate that belimumab exposure, efficacy and safety observed in Western paediatric population is similar to that observed in Chinese and Western adults.

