10.12. Appendix 12: Protocol Amendment History

Amendment 01 (29 January 2021)

Overall Rationale for the Amendment:

This amendment specifies the criteria for primary efficacy evaluation and sample size consideration and for this criteria, adjusts the screening laboratory test for latent tuberculosis, removes the volume of blood samples for PK analysis, defines the tests conducted before informed consent would not be utilized for screening or baseline purpose, clarifies dose strength of the study intervention; specifies non-serious related AE reporting method. Additionally the following changes have been added: addition of wording to allow a repeat laboratory test for screening; requirement on recording the actual date and time of PK sample; addition of “CPK” in clinical chemistry test, clarification that PK sample will be collected when liver event happens, and addition of the missing items to the SoA according to the exclusion criteria and screening assessments.

Section # and Name	Description of Change	Brief Rationale
1.2 SoA: Safety Assessments	Addition of chest X-ray examination at screening visit.	Chest X-ray as an examination to rule out latent tuberculosis infection has not been defined in the SoA.
1.2 SoA: Laboratory Assessments	Replacement of "TSPOT" test by "QuantiFERON-TB Gold Plus" test.	The central lab only provides "QuantiFERON-TB Gold Plus" test, which has similar efficacy as "TSPOT" test in ruling out latent tuberculosis infection.
5.2 Exclusion Criteria	Replacement of "TSPOT" test by "QuantiFERON-TB Gold Plus" in exclusion criterion #25	To accommodate the availability of "QuantiFERON-TB Gold Plus" test in central lab.
5.5 Repeat Assessments during the 35 Day Screening Period	Addition of the wording to allow repeat laboratory test for screening purpose.	To reduce the probability of rescreening in cases of technical malfunction; or a value close enough to the exclusionary threshold that it may reasonably lie within the degree of variability of the assay; or if there is reason to believe the result may be false by investigator.
6.1 Study Intervention(s) Administered	Removal of the dose strength of "20 mL vial containing 400 mg lyophilised belimumab" from the table and the main content.	To clarify the dose strength used in this study.

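### Does the placebo-rate target of 43.6% in Protocol section 9.1 clash with the efficacy comparisons named in sections 4.2 and 9.4.2.1?

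*Protocol*

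**What the plan says.** Section 9.1 plans a descriptive analysis without formal inference. For the primary efficacy endpoint (a SELENA SLEDAI reduction of at least 4 points at Week 52) it takes the BEL114055 placebo response as a guide: "The target can be described as the observed proportion of patients with clinical benefit" is to be above 43.6%.

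Section 9.2 assumes a response rate of 54.7%, taken from BEL114055, and states that "a study with 65 participants will have more than 95.0% probability to observe a percentage larger than 43.6" per cent.

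Section 9.4.2.1 plans the frequency, percentage and 95% CI. It adds that the corresponding BEL114055 results "will be used to guide the evaluation of consistency for this efficacy endpoint collected on Chinese subjects". It names neither an arm nor a criterion.

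Section 4.2 says in its design rationale that the study is "to demonstrate that belimumab exposure, efficacy and safety observed in Western paediatric population is similar to that observed in Chinese and Western adults". Section 2.1 puts the exposure question differently: "to demonstrate if exposure in Chinese paediatric SLE patients is similar to SLE paediatric patients in Western countries".

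The Amendment 01 entry in section 10.12 lists "Addition of the target value of the primary efficacy endpoint" and gives compliance with an authority's requirement as the reason.

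**The concern.** Every participant receives belimumab, so a reader expects consistency with BEL114055 to mean consistency with its belimumab arm. The only number in section 9.1 is that study's placebo rate, compared with a bare point estimate and no margin. A rate 1 point above placebo and 10 points below the planning rate would count as reaching the target. The sentence in section 4.2 adds a third comparison, Western children against adults, on which this study collects no data. It also uses the language of demonstration, which does not suit a descriptive study.

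The study supports a registration. If the report said that the target was met on 29 to 31 responders, readers might take this as agreement with the earlier belimumab result when it shows only that the observed rate is above the earlier placebo rate.

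**Working it through.** **Inputs.** n = 65 and planning rate 54.7% (section 9.2); target above 43.6% (section 9.1). Section 9.2 does not say which arm gave 54.7%. It equals 29/53, and the same section gives 53 participants in the 10 mg/kg arm, so it is taken here as the belimumab rate.

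**1. Smallest count that meets the target.** 0.436 × 65 = 28.34, so 29 responders are needed (28/65 = 43.1%, 29/65 = 44.6%).

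**2. The plan's own figures.** With X binomial(65, p), P(X ≥ 29) is the sum over k = 29 to 65 of C(65,k) p^k (1−p)^(65−k).

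- At p = 0.547 it is 0.960. The stated probability of more than 95.0% reproduces. So does the exact interval of 41.9% to 67.1% at 54.7%.
- At p = 0.436 it is 0.482. The protocol does not give this figure.

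**3. The stretch nearer to placebo.** The midpoint is (43.6 + 54.7)/2 = 49.15%, and 0.4915 × 65 = 31.95. The first count nearer to 54.7% is therefore 32.

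| Responders | Rate | Points from 43.6% | Points from 54.7% | Exact 95% CI |
|---|---|---|---|---|
| 29 | 44.6% | 1.0 | 10.1 | 32.3% to 57.5% |
| 30 | 46.2% | 2.6 | 8.6 | 33.7% to 59.0% |
| 31 | 47.7% | 4.1 | 7.0 | 35.1% to 60.5% |
| 32 | 49.2% | 5.6 | 5.5 | 36.6% to 61.9% |
| 36 | 55.4% | 11.8 | 0.7 | 42.5% to 67.7% |
| 37 | 56.9% | 13.3 | 2.2 | 44.0% to 69.2% |

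P(X ≥ 32) is 0.844 at 54.7% and 0.214 at 43.6%. Hence P(29 to 31) = 0.960 − 0.844 = 0.116 at 54.7%, and 0.482 − 0.214 = 0.268 at 43.6%.

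**4. Would another cut separate the two rates?** From 29 to 36 responders every interval contains both 43.6% and 54.7%. A result of 31 is thus no less compatible with the belimumab rate than a result of 32. The lower limit first passes 43.6% at 37 responders. A rule set there would be met with probability 0.408 at 54.7% and 0.021 at 43.6%. With 65 participants, no cut gives both a high chance of success at the planning rate and a low one at the placebo rate:

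| Rule | Met at 54.7% | Met at 43.6% |
|---|---|---|
| 29 or more (section 9.1) | 96% | 48% |
| 32 or more (midpoint) | 84% | 21% |
| 37 or more (lower CI limit above 43.6%) | 41% | 2% |

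**5. The texts side by side.** Section 9.1 asks whether the observed rate is above the earlier placebo rate. Section 9.4.2.1 introduces its consistency look as a further step. Both use BEL114055 as guidance for a descriptive analysis, and neither says that passing 43.6% establishes consistency. The section 4.2 sentence covers exposure, efficacy and safety together and names no endpoint or threshold. The primary objective later in section 4.2, section 2.1, the objectives table in section 3 and section 9.4.2.1 all name Chinese paediatric patients.

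**The case for a change.** The case for a change is that the protocol itself fixes the target and builds it into the sample-size argument, so an unseen SAP does not remove it. The protocol reports only the favourable probability (above 95%) and not the 48% at a placebo-level rate. The section 4.2 sentence is current text and wrong as written. A modest repair seems available: keep 43.6% as a minimum and name 32 of 65 as the level to be called consistent.

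Part of this stands. The section 4.2 sentence misnames the populations, the floor is weak, and passing it does not show agreement with the belimumab arm.

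The repair does not stand. A cut at 32 is again a point-estimate rule without a margin. It rests on a midpoint that has no clinical or regulatory basis in the protocol, and it divides 31 from 32 where the data cannot. It would lower the planned probability from 96% to 84%, so the statement in section 9.2 would not hold for it. It would also put a pass-or-fail label on a deliberately descriptive assessment. Replacing the value outright would touch a figure that the amendment log attributes to an authority. How consistency is judged is detail that a protocol commonly leaves to the SAP.

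**Conclusion.** No change to the plan follows. The target in section 9.1 is a lenient descriptive floor against placebo: 29 of 65 suffices, with probability 96% at a true rate of 54.7% and 48% at 43.6%. It is compatible with the consistency look in section 9.4.2.1, because both can be reported for the same result. The planned 95% CI guards against over-reading. At 29 responders it runs from 32.3% to 57.5%, which shows that the data fit both the placebo and the planning rate.

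The section 4.2 wording is a clerical slip in rationale text. Objectives, endpoints and analyses are correctly stated elsewhere, and nothing the trial does or concludes depends on that sentence.

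This rests on three assumptions: that 54.7% is the belimumab rate; that 43.6% is the placebo rate for this endpoint, as section 9.1 says (section 2.2.2 gives the same figure for placebo SRI response, and the protocol does not say whether the two coincide); and that all 65 participants form the denominator.
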